5.2 Exclusion Criteria

If an individual meets any of the following criteria, he or she is ineligible for this study:

5.2.1 General Exclusion Criteria

- 1. Individuals involved in the conduct of the study, their employees, or immediate family members of such individuals.
- 2. Any condition that, in the opinion of the Investigator or the Sponsor/Central Review Committee, would interfere with evaluation of the IP or interpretation of participant safety or study results (including borderline disease activity).
- 3. History of allergy, hypersensitivity reaction, or anaphylaxis to any component of the IP or to a previous mAb or human Ig therapy.
- 4. Participation in another clinical study with an investigational drug within 4 weeks prior to Day 1 or within 5 published half-lives, whichever is longer (also refer to Section 5.2.3).
- 5. Breastfeeding or pregnant women or women who intend to become pregnant anytime from signing the ICF through 3 months after receiving the last dose of IP.

^a A change in birth control method is allowed during the study. If a change occurs, unless the patient is changing the method to complete abstinence, the patient must employ a barrier method in addition to the highly effective method of contraception for at least two months.

^b This is also considered to be a hormonal method.

^c A vasectomized partner is a highly effective method of birth control provided that partner is the sole sexual partner of the woman of childbearing potential study participant and that the vasectomized partner has received medical assessment of the surgical success.

^d Sexual abstinence is considered to be a highly effective method only if defined as refraining from heterosexual intercourse during the entire period of the study and if it is the preferred and usual lifestyle of the participant.

^e Progestogen-only hormonal contraception where inhibition of ovulation is not the primary mode of action (minipill) is not accepted as a highly effective method.

- 6. History of drug or alcohol abuse that, in the opinion of the Investigator, might affect participant safety or compliance with visits, or interfere with other study assessments.
- 7. Major surgery within 8 weeks prior to Screening or elective surgery planned from Screening through Day 393.
- 8. Spontaneous or induced abortion, still or live birth, or pregnancy ≤ 4 weeks prior to Screening.
- 9. Known history of a primary immunodeficiency or an underlying condition such as known human immunodeficiency virus (HIV) infection, a positive result for HIV infection per central laboratory, splenectomy, or any underlying condition that in the opinion of the Investigator significantly predisposes the participant to infection.
- 10. At Screening, any of the following per central laboratory (tests may be repeated once within the same Screening period to confirm results prior to Randomization):
- Aspartate aminotransferase (AST) $> 2.5 \times$ upper limit of normal (ULN)
- Alanine aminotransferase (ALT) $> 2.5 \times ULN$
- Total bilirubin > 1.5× ULN (unless due to Gilbert's syndrome)
- Serum IgG < 600 mg/dL (or < 6 g/L)
- Neutrophil count < $1000/\mu L$ (or < $1.0\times10^9/L$) or < $500/\mu L$ (< $0.5\times10^9/L$) if due to active SLE
- Platelet count $< 50,000/\mu L$ (or $< 50 \times 10^9/L$) or $< 25,000/\mu L$ ($< 25 \times 10^9/L$) if due to active SLE
- Hemoglobin $\leq 8 \text{ g/dL}$ (or $\leq 80 \text{ g/L}$) or $\leq 7 \text{ g/dL}$ ($\leq 70 \text{ g/L}$) if due to active SLE
- Glycosylated hemoglobin > 8% (or > 0.08)
- Total lymphocyte count < 200 cells/mm³
- Glomerular filtration rate < 30 mL/min/1.73 m²
- Spot UPCr > 3 mg/mg (> 339 mg/mmol)
- 11. Confirmed positive test for hepatitis B serology defined as:
- Hepatitis B surface antigen (HBsAg), or
- Hepatitis B core antibody (HBcAb) AND hepatitis B virus (HBV) DNA detected above the lower limit of quantitation (LLOQ) by reflex testing by the central laboratory at Screening.

Note that participants who are HBcAb positive at Screening will be tested every 3 months for HBV DNA. Study drug will be discontinued if the participant's HBV DNA levels are confirmed to exceed the LLOQ as per the central laboratory.

- 12. Positive test for hepatitis C virus antibody.
- 13. Active TB, or a positive IFN-gamma release assay (IGRA) test at Screening, unless documented history of appropriate treatment for active or latent TB.

Note that participants with an indeterminate IGRA test result with well-documented previous treatment do not need to repeat testing and are eligible for randomization. Participants with an indeterminate IGRA test result without previous treatment can repeat the test, but if the repeat test is also indeterminate, they are excluded.

14. Any severe herpes virus family infection (including Epstein-Barr virus, cytomegalovirus [CMV]) at any time prior to Randomization, including, but not limited to, disseminated

- herpes, herpes encephalitis, recent recurrent herpes zoster (defined as 2 episodes within the last 2 years), or ophthalmic herpes.
- 15. Any herpes zoster, CMV, or Epstein-Barr virus infection that was not completely resolved 12 weeks prior to Randomization.
- 16. Any of the following within 30 days prior to signing the ICF and though Randomization:
- Clinically significant active infection in the opinion of the Investigator, including ongoing, and chronic infection requiring antibiotics or antiviral medication (chronic nail infections are allowed).
- Any infection requiring hospitalization or treatment with IV anti-infectives.
- A participant with a documented positive SARS-CoV-2 test may be rescreened at least 2 weeks after a positive test if the participant is asymptomatic and at least 3 weeks after symptomatic COVID-19 illness.
- 17. Opportunistic infection requiring hospitalization or parenteral antimicrobial treatment within 2 years prior to Randomization (Appendix 3).
- 18. Any acute illness or evidence of clinically significant active infection,
- 19. Clinically significant cardiac disease including unstable angina and/or myocardial infarction and/or congestive heart failure within 6 months prior to Randomization. Any cardiac condition including, but not limited to the following, if in the opinion of the Investigator or Medical Monitor, would increase the risk of study participation:
- Inadequately controlled arrhythmia.
- Presence of clinically significant abnormality on ECG.
- 20. History of cancer within the past 5 years, except as follows:
- In situ carcinoma of the cervix treated with apparent success with curative therapy > 12 months prior to Screening, or
- Cutaneous basal cell or squamous cell carcinoma treated with apparent success with curative therapy.
- 21. Receipt of a live-attenuated vaccine within 4 weeks prior to Day 1. Administration of inactivated (killed) vaccines is acceptable.
- 22. Participant should be assessed for epidemiologic risk of COVID-19 (ie, recent exposure, high-risk housing) and for health-related risk of COVID-19 severity based on current understanding of risk factors for severe disease when making a decision regarding the individual's risk of participation. Participants who have COVID-19 or other significant infection, or in the judgment of the Investigator, may be at a high risk of COVID-19 or its complications should not be randomized.

5.2.2 Disease-Related Criteria

23. Active LN OR active severe or unstable neuropsychiatric SLE (eg, aseptic meningitis, cerebral vasculitis, myelopathy, demyelination syndromes [ascending, transverse, acute inflammatory demyelinating polyradiculopathy], acute confusional state, impaired level of consciousness, psychosis, acute stroke or stroke syndrome, cranial neuropathy, status epilepticus, cerebellar ataxia, and mononeuritis multiplex) where, in the opinion of the Investigator or Medical Monitor, protocol-specified SoC is insufficient and utilization of a more aggressive therapeutic approach, such as IV cyclophosphamide, high-dose IV pulse GC therapy, MMF of > 3 gm/day (MPA of > 2.16 gm/day), or an increase from

- baseline dose of MMF/MPA and/or other treatments not permitted in the protocol, may be indicated.
- 24. Current diagnosis of non-SLE vasculitis syndrome, mixed connective tissue disease, or rheumatic (overlap) syndrome that may confound clinical assessments in the study (eg, scleroderma/systemic sclerosis). Secondary sicca or Sjögren's syndrome, antiphospholipid antibody syndrome, and overlap with myositis or rheumatoid arthritis without erosive joint disease ("rhupus") are allowed provided the participant also meets the criteria for classification as SLE. A history of mixed connective tissue disease that over time has developed into a diagnosis of SLE is permitted provided diagnosis of SLE has been present for at least 6 months.
- 25. History of antiphospholipid syndrome (APS) with thromboembolic event within 6 months of Screening or not on an adequate anticoagulation regimen in the 6 weeks prior to or at Screening in the opinion of the Investigator. However, presence of antiphospholipid antibodies alone (without a history of thromboembolic event) is not exclusionary.
- 26. Current inflammatory joint or skin disease other than SLE that, in the opinion of the Investigator, could interfere with the inflammatory arthritis or skin assessments and confound the disease activity assessments.

5.2.3 Prior and Concomitant Therapy Criteria

- 27. Unstable dosing or initiation of a regularly used nonsteroidal anti-inflammatory drug (NSAID) within 2 weeks prior to Baseline (Day 1) other than low-dose [≤ 350 mg] aspirin for cardiovascular prophylaxis or for APS, which is permitted. Non-regular use of NSAID for pain control is permitted.
- 28. Receipt of any of the following treatments within the following timeframes. Refer to Section 7.4.1 for more details:
- 2 Weeks prior to Screening and through Randomization:
 - Initiation of or unstable dosing of topical therapy (eg, GCs, calcineurin inhibitors) for cutaneous lupus (cyclosporine eye drops are permitted).
 - $-\,$ Opioid use above 40 mg/day morphine-equivalent, unstable dosing, or initiation of regular dosing.
- 4 Weeks prior to Screening and through Randomization:
 - Intra-articular therapies, such as GCs.
 - Systemic GC doses of \geq 100 mg prednisone or equivalent or intramuscular, IV or intralesional GCs.
 - Intradermal GC for alopecia.
 - IV, intramuscular, or SC Ig.
 - Other non-biologic immunosuppressive agents (eg, dapsone, danazol, calcineurin inhibitors, sulfasalazine, mizoribine, mechanistic target of rapamycin inhibitors, retinoids, thalidomide, lenalidomide, adrenocorticotropic hormone [ACTH] analogs, dehydroepiandrosterone), or Janus kinase inhibitors.
 - Transfusion with blood, packed red blood cells, platelets or treatment with plasmapheresis, plasma exchange, or Therakos® photopheresis.

- 12 Weeks (or 5 half-lives, whichever is longer) prior to Randomization:
 - Cyclophosphamide or alkylating agents (eg, chlorambucil).
 - Cytokine or cytokine receptor antagonists, including but not limited to interleukin (IL)-1, IL-6, IL-17, IL-12/23, IL-23, IFN, integrin, or TNFα antagonists (except for IFNα kinoid, for which receipt at any time is exclusionary).
 - Belimumab, abatacept, or eculizumab.
 - Other biologics used for immunosuppression or immunomodulation (eg, IFN therapy, IL-2).
 - Investigational drugs.
 - IPP-201101 (Lupuzor™).
- 24 Weeks prior to Randomization:
 - B cell-depleting therapies (eg, rituximab, ocrelizumab, ofatumumab, inebilizumab, telitacicept) other than atacicept or obinutuzumab.
 - Receipt of systemic GCs for more than a total of 2 weeks for any concurrent illness, including asthma, inflammatory bowel disease, or drug-induced SLE.
 - O Systemic is defined as PO, rectal, or any injectable route of administration.
- 40 Weeks prior to Randomization:
 - Atacicept.
- 1 Year prior to Randomization:
 - Bacille-Calmette-Guerin (BCG) vaccination.
- 1.5 Years prior to Randomization:
 - Obinutuzumab.

5.3 Rescreening Procedures

Participants may be rescreened once after a screen failure for inadequate disease activity or other reason which, in the opinion of the Investigator, may change to make the participant eligible. A participant who rescreens will be required to re-sign the ICF. A screen failure is a consented participant who has been deemed ineligible on the basis of one or more eligibility criteria or who has withdrawn consent prior to treatment assignment. Participants who rescreen within 8 weeks of signing the ICF do not have to repeat serum virology, TB assessment, or chest X-ray if performed within 12 weeks, or, if relevant, FSH testing.

5.4 Replacement of Participants

Participants who have been randomized but not dosed will not be followed to completion of the study and may be replaced at the discretion of the Sponsor.

6 STUDY CONDUCT

6.1 General Instructions

Participants will undergo a Screening period of approximately 4 weeks (Days -28 to -1), Randomization on Day 1, treatment and assessments through Week 48, and a SFU period of 8 weeks (through Week 56).

6.2 Schedule of Study Assessments

Table 2, Table 3, and Table 4 summarize the Screening, treatment, and follow-up assessments and procedures.

 Table 2
 Screening Procedures

Study Day	-28 to -1
Visit Number	1
General Assessments	1
Informed consent	X
Eligibility review	X
Demographic data	X
Review of SLE and other medical history, medications, and surgery/procedures	X
Documentation of SLE classification criteria	X
Chest X-ray ^a	X
TB assessment ^b	X
12-lead ECG (after 10 minutes rest in supine position) °	X
Vital signs, height, and weight ^d	X
Physical examination ^e	X
BILAG 2004 assessments, SLEDAI-2K, CLASI, PGA,	X
Laboratory Assessments	
Pregnancy (serum βhCG) test (in women of childbearing potential)	X
FSH (to confirm postmenopausal status, as appropriate) ^g	X
Serum virology h	X
Routine hematology and chemistry i	X
HbA1c	X
Urinalysis and spot UPCr (aim to collect urine sample at same time of day, if possible) j	X
Anticardiolipin antibodies (IgG, IgA, and IgM)	X
Anti-β2GP1 antibody	X
Lupus anticoagulant	X
Haptoglobin ^k	X
C3 and C4	X
PT/INR and PTT	X

Table 2 Screening Procedures

Study Day	-28 to -1
Visit Number	1
Serum IgG, IgA, IgM	X
Questionnaires ¹	
Safety	
Concomitant medications	X
AEs, SAEs, and/or AESIs	X

AE: adverse event; AESI: AE of special interest;

Isles Lupus Assessment Group; C: complement;

CLASI: Cutaneous Lupus Erythematosus Disease Area and Severity Index:

ECG: electrocardiogram; FSH: follicle-stimulating hormone; HbA1c: glycosylated hemoglobin;

Ig: immunoglobulin; INR: international normalized ratio;

PTT: partial thromboplastin time; SAE: serious AE; SLE: systemic lupus erythematosus; SLEDAI-2K: SLE Disease Activity Index 2000; TB: tuberculosis; UPCr: urine protein:creatinine ratio;

X: to be performed.

^a The results of a chest X-ray (posterior-anterior, anterior-posterior, and lateral views) performed within 12 weeks of the Screening visit (if available) are acceptable, provided there is no reason to suspect any clinical changes. The chest X-ray may be completed anytime during the Screening period as long as all results have been reviewed by the Investigator prior

to Randomization. If the chest X-ray is performed at Screening, posterior-anterior and lateral views should be evaluated,

- unless where prohibited by local health authority. Magnetic resonance imaging or computed tomography scans of the chest performed within 12 weeks of the Screening visit are acceptable.

 ^b The results of an IFN-gamma release assay (ie, QuantiFERON-TB Gold Plus or T-SPOT) performed within 12 weeks of the
- Screening visit (if available) are acceptable, provided there is no reason to suspect any re-exposure. c Should be performed after vital signs are collected.
- ^d Vital signs include systolic and diastolic blood pressure obtained after at least 5 minutes at rest in a seated position, heart rate, respiratory rate (breaths/min), and body temperature. Height will be measured at Screening only.
- ^e A focused physical examination should be performed. A focused physical examination should always include assessment of head, ears, eyes, nose, throat, lungs, heart, abdomen, skin, and extremities.
- ^f Additional assessments, (eg, ECG or chest radiograph) should be performed as needed to fully obtain information needed for the BILAG 2004 Index and and/or SLEDAI-2K assessments. Assessments at Screening should be compared to previous lupus disease and medical history, as appropriate.
- g FSH testing does not have to be repeated if performed within 12 weeks prior to Screening (eg, re-Screening).
- h Includes human immunodeficiency virus testing, hepatitis B testing (hepatitis B surface antigen and hepatitis core antibody [HBcAb] with reflex DNA testing), and hepatitis C virus antibody testing. Participants who are HBcAb positive with a negative hepatitis B virus (HBV) DNA at Screening will be tested every 3 months for HBV DNA. To remain eligible for the study, the participant's HBV DNA levels must be confirmed to remain below the lower limit of quantitation as per the central laboratory. Serum virology does not have to be repeated if performed within 12 weeks prior to Screening (eg, re-Screening).
- $^{\rm i}$ Refer to Table 5 for a list of routine laboratory assessments.
- ^j Urine collection can be postponed for up to 14 days in women with menstrual bleeding or a urinary tract infection at the scheduled visit.
- ^k Haptoglobin will be collected during Screening but will only be tested if needed to confirm suspected hemolytic anemia.
- ¹ Questionnaires are strongly recommended to be completed before any other procedures are performed.

 Table 3
 Schedule of Assessments During the Treatment Period

Study Day	1	29	57	85	113	141	169	197	225	253	281	309	337
Visit Window (± days)	-	3	3	3	3	3	3	3	3	3	3	3	3
Study Week	0	4	8	12	16	20	24	28	32	36	40	44	48/ET
Visit Number	2	3	4	5	6	7	8	9	10	11	12	13	14
General Assessments/Procedures						•					•		
12-lead ECG (after 10 minutes rest in supine position) ^a							X						X
Vital signs and weight ^b	X	X	X	X	X	X	X	X	X	X	X	X	X
Physical examination ^c	X	X	X	X	X	X	X	X	X	X	X	X	X
BILAG 2004 assessments, SLEDAI-2K, CLASI, PGA, and Joint Count $^{\rm d}$	X	X	X	X	X	X	X	X	X	X	X	X	X
Eligibility review ^e	X												
Randomization	X												
Laboratory Assessments						•	•				•		
Pregnancy (urine) test ^f	X	X	X	X	X	X	X	X	X	X	X	X	X
Hepatitis B DNA testing ^g	X			X			X			X			X
Routine hematology and chemistry h	X	X	X	X	X	X	X	X	X	X	X	X	X
HbA1c							X						X
Lipids (after an 8-hour fast; water allowed) i	X						X						X
Urinalysis and spot UPCr (aim to collect urine sample at same time of day, if possible) ^j	X	X	X	X	X	X	X	X	X	X	X	X	X
Confirmatory tests for hemolytic anemia and active APS k	X	X	X	X	X	X	X	X	X	X	X	X	X
Anticardiolipin antibodies (IgG, IgA, IgM)	X			X			X			X			X
Anti-β2GP1 antibody	X			X			X			X			X
Lupus anticoagulant ¹							X						X
C3 and C4	X	X	X	X	X	X	X	X	X	X	X	X	X

 Table 3
 Schedule of Assessments During the Treatment Period

Study Day	1	29	57	85	113	141	169	197	225	253	281	309	337
Visit Window (± days)	-	3	3	3	3	3	3	3	3	3	3	3	3
Study Week	0	4	8	12	16	20	24	28	32	36	40	44	48/ET
Visit Number	2	3	4	5	6	7	8	9	10	11	12	13	14
PT/INR and PTT	X			X			X			X			X
Serum IgA, IgG, and IgM	X			X			X			X			X
hs-CRP	X			X			X			X			X
pDC FACS	X	X	X	X		X	X		X	X		X	X
Whole blood transcriptomics	X	X		X			X			X			X
PBMC cytometry	X						X						X
VIB7734 PK (serum)	X	X	X	X	X	X	X	X	X	X	X	X	X

SLEDAI-

Table 3 Schedule of Assessments During the Treatment Period

Study Day	1	29	57	85	113	141	169	197	225	253	281	309	337
Visit Window (± days)	-	3	3	3	3	3	3	3	3	3	3	3	3
Study Week	0	4	8	12	16	20	24	28	32	36	40	44	48/ET
Visit Number	2	3	4	5	6	7	8	9	10	11	12	13	14
Investigational Product Administration													
IP administration	X	X	X	X	X	X	X	X	X	X	X	X	
Safety			•				•	•					
Local injection tolerability	X	X	X	X	X	X	X	X	X	X	X	X	X
Concomitant medications	X	X	X	X	X	X	X	X	X	X	X	X	X
AEs, SAEs, and/or AESIs	X	X	X	X	X	X	X	X	X	X	X	X	X

AE: adverse event; AESI: AE of special interest glycoprotein 1; BILAG: British Isles Lupus Assessment Group; C: complement;

CLASI: Cutaneous Lupus Erythematosus Disease Area and Severity Index: ECG: electrocardiogram; ET:

Early Termination; FACS: fluorescence-activated cell sorting;

HbA1c: glycosylated hemoglobin; hs-CRP: high-sensitivity C-reactive protein; Ig: immunoglobulin;

normalized ratio; IP: investigational product;
PBMC: peripheral blood mononuclear cells; pDC: plasmacytoid dendritic cell; PGA: Physician Global Assessment;
PK: pharmacokinetic(s);

cell; PGA: Physician Global Assessment;
PT: prothrombin time;
PTT: partial thromboplastin time;
SAE: serious AE;

2K: Systemic Lupus Erythematosus Disease Activity Index 2000;

UPCr: urine protein:creatinine ratio; X: to be performed.

All collections and assessments should be performed predose on days when IP is administered, unless otherwise specified.

^a Should be performed after vital signs are collected.

^b Vital signs include systolic and diastolic blood pressure obtained after at least 5 minutes at rest in a seated position, heart rate, respiratory rate (breaths/min), and body temperature.

^c A focused physical examination should be performed at all visits, except during the Baseline (Day 1), Week 48, or Early Termination visits. A focused physical examination should always include assessment of head, ears, eyes, nose, throat, lungs, heart, abdomen, skin, and extremities.

^d Additional assessments, (eg, ECG or chest X-ray) should be performed as needed to fully obtain information needed for the BILAG and and/or SLEDAI-2K assessments.

e Participant eligibility (based on Screening assessments, including non-laboratory-based assessments at Baseline [Day 1] as per the inclusion and exclusion criteria [Section 5]) must be checked again on Day 1 prior to Randomization.

^f Women of childbearing potential as defined in Inclusion Criteria #8.

^g Reflex DNA testing if isolated hepatitis B core positive at Screening.

 Table 3
 Schedule of Assessments During the Treatment Period

Study Day	1	29	57	85	113	141	169	197	225	253	281	309	337
Visit Window (± days)	-	3	3	3	3	3	3	3	3	3	3	3	3
Study Week	0	4	8	12	16	20	24	28	32	36	40	44	48/ET
Visit Number	2	3	4	5	6	7	8	9	10	11	12	13	14

h Refer to Table 5 for a list of routine laboratory assessments.

ⁱ This visit recommended to occur in the morning.

^j Urine collection can be postponed for up to 14 days in women with menstrual bleeding or a urinary tract infection at the scheduled visit.

k Serum aliquots will be used for the BILAG confirmatory tests, including haptoglobin if needed to confirm suspected hemolytic anemia, and anticardiolipin antibodies (IgG, IgA, and IgM) and anti-β2GP1 antibody if needed to confirm suspected APS.

¹ If an active manifestation of APS is suspected, the lupus anticoagulant should be collected and tested at all relevant study days, in addition to those already indicated in the schedule of assessments during the Treatment period.

^m Questionnaires are strongly recommended to be completed before any other procedures are performed.

Table 4 Schedule of Assessments During the Safety Follow-Up Period

Study Day	365	393
Visit Window (± Days)	7	7
Study Week	52	56
Visit Number	15	16
General Assessments	1	1
12-lead ECG (after 10 minutes rest in supine position) ^a		X
Vital signs and weight ^b	X	X
Physical examination ^c	X	X
BILAG 2004 Index assessments, SLEDAI-2K, CLASI, PGA,	X	X
Laboratory Assessments		
Pregnancy (urine) test ^e	X	X
Hepatitis B DNA testing ^f		X
Routine hematology and chemistry ^g	X	X
HbA1c		X
Lipids (after an 8-hour fast; water allowed) h		X
Urinalysis and spot UPCr (aim to collect urine sample at same time of day, if possible) i	X	X
Confirmatory tests for hemolytic anemia and active APS ^j	X	X
Anticardiolipin antibodies (IgG, IgA, and IgM)		X
Anti-β2GP1 antibody		X
Lupus anticoagulant ^k		X
C3 and C4	X	X
PT/INR and PTT		X
Serum IgA, IgG, and IgM		X
hs-CRP	X	X
pDC FACS	X	X
PBMC cytometry		X
VIB7734 PK (serum)	X	X
Questionnaires ¹		

Table 4 Schedule of Assessments During the Safety Follow-Up Period

Study Day	365	393
Visit Window (± Days)	7	7
Study Week	52	56
Visit Number	15	16
Safety		
Concomitant medications	X	X
AEs, SAEs, and/or AESIs	X	X

AE: adverse event; AESI: AE of special interest;

APS: antiphospholipid syndrome; β2GP1: β2-glycoprotein 1; BILAG: British Isles Lupus Assessment Group; C: complement; CLASI: Cutaneous Lupus Erythematosus Disease Area and Severity Index; ECG: electrocardiogram; FACS: fluorescence-activated cell sorting;

HbA1c: glycosylated hemoglobin; hs-CRP: high-sensitivity C-reactive protein;

Ig: immunoglobulin; INR: international normalized ratio;

PBMC:

peripheral blood mononuclear cells; pDC: plasmacytoid dendritic cell; PGA: Physician Global Assessment; PK: pharmacokinetic(s); PT: prothrombin time;

PTT: partial thromboplastin time; SAE: serious AE; SLEDAI-2K: Systemic Lupus Erythematosus Disease Activity Index 2000; UPCr: urine protein:creatinine ratio; X: to be performed., Safety Follow-Up visits will be conducted at 4 and 8 weeks after the last dose of investigational product (IP) for participants who have completed the 48-week Treatment period. These assessments, however, will not be performed on participants who enter the long-term extension study.

- Participants who permanently discontinue IP at any point in the study but who **do not** withdraw consent of study participation will complete all study visits through Study Week 48/ET and at least 12 weeks follow up after the last dose of IP. Participants who permanently discontinue IP at any point in the study and who **do** withdraw consent of study participation will only complete the Study Week 48/ET assessments (if they agree to do so before withdrawing consent).
- ^a Should be performed after vital signs are collected.
- ^b Vital signs include systolic and diastolic blood pressure obtained after at least 5 minutes at rest in a seated position, heart rate, respiratory rate (breaths/min), and body temperature.
- ^c A focused physical examination should be performed. A focused physical examination should always include assessment of head, ears, eyes, nose, throat, lungs, heart, abdomen, skin, and extremities.
- ^d Additional assessments, (eg, ECG, or chest radiograph) should be performed as needed to fully obtain information needed for the BILAG 2004 Index and and/or SLEDAI-2K assessments.
- ^e Women of childbearing potential as defined in Inclusion Critertia #8.
- f Reflex DNA testing if isolated hepatitis B core positive.
- ^g Refer to Table 5 for a list of routine laboratory assessments.
- ^h This visit recommended to occur in the morning.
- ⁱ Urine collection can be postponed for up to 14 days in women with menstrual bleeding or a urinary tract infection at the scheduled visit.
- j Serum aliquots will be used for the BILAG confirmatory tests, including haptoglobin if needed to confirm suspected hemolytic anemia, and anticardiolipin antibodies (IgG, IgA, and IgM) and anti-β2GP1 antibody if needed to confirm suspected APS.
- k If an active manifestation of APS is suspected, the lupus anticoagulant should be collected and tested at both Study Days 365 and 393.
- ¹ Questionnaires are strongly recommended to be completed before any other procedures are performed.

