6.4.4 Participants Lost to Follow-up

Participants will be considered lost to follow-up only if no contact has been established by the time the study is completed and such that there is insufficient information to determine the participant's status at Day 393/Visit 16. A participant is considered lost to follow-up when 3 documented attempts at contact (with one documented attempt being registered letter/certified mail) are unsuccessful:

- Registered letter/certified mail.
- Phone calls, text messages, or emails.
- Consulting publicly available sources, if allowed by local regulations, to determine the status of the participant.

"Lost to follow-up" as a reason for study discontinuation must be documented by time and date of telephone calls, emails, text messages, numbers called, individuals spoken to if not the participant, documentation that a certified/registered letter was sent, and documentation of publicly available sources that were consulted.

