8.2.3 Pregnancy

Pregnancy in a woman who has received IP must be reported to Sponsor from time of signed ICF until end of study follow-up or 3 months (approximately 5 half-lives) following the last dose of IP in case of early withdrawal (Section 8.3).

Participants who become pregnant during the study period must not receive additional doses of IP but will not be withdrawn from the study. If the participant requests to know which treatment she received, this information will be provided to her. The pregnancy will be followed for outcome of the mother and child (including any premature terminations) and should be reported to the Sponsor after outcome.

Should the Investigator become aware of a pregnancy in the partner of a male study participant who has received IP, this should be reported to Sponsor within 24 hours of knowledge of the event, by fax or email using the Pregnancy Report Form (refer to Section 8.3 for contact information). The Sponsor will endeavor to collect follow-up information on such pregnancies, provided the partner of the study participant provides consent for disclosure of their information.

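### The Table 4 footnote times safety follow-up at 4 and 8 weeks after the last dose, but Table 4's own visit days fall 8 and 12 weeks after the last scheduled dose.

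*Protocol*

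**What the plan says.** All of the following is current protocol text.

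- **Dosing (Protocol 6.2, Table 3).** IP is given at 12 visits, every 4 weeks from Week 0 to Week 44. Week 44 is Day 309. The Week 48 column (Day 337) has no IP administration. Section 4.1 is consistent with this, since it treats stopping before Week 44 as premature.
- **Follow-up visits (Table 4).** The header rows read "Study Day 365 393" and "Study Week 52 56", with "Visit Window (± Days) 7 7".
- **Footnote to Table 4.** "Safety Follow-Up visits will be conducted at 4 and 8 weeks after the last dose of investigational product (IP"), and the sentence is limited to visits "for participants who have completed the 48-week Treatment period". Participants who enter the extension study do not have these visits.
- **Next paragraph of the same footnote, repeated in 6.4.3.** Participants who stop IP for good but do not withdraw consent attend all visits through Week 48 and have at least 12 weeks of follow-up after their last dose.
- **Length of the period.** Section 6.1 gives "a SFU period of 8 weeks (through Week 56"). The synopsis, Protocol 4.1 and SAP 2.2 say the same. Section 6.4.4 judges loss to follow-up by "status at Day 393/Visit 16", and exclusion criterion 7 also runs to Day 393.

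**The concern.** The footnote and the columns it annotates give different intervals from the last dose to the same two visits. Both cannot be followed.

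The footnote states a rule in the assessment schedule, so the choice has consequences. Section 8.2 collects adverse events up to the final study visit. Day 393 is the only visit after Week 48 at which Table 4 schedules an ECG, hepatitis B DNA, HbA1c, lipids, coagulation tests, serum immunoglobulins, antiphospholipid tests and PBMC cytometry. Pregnancy reporting (8.2.3) runs "until end of study follow-up or 3 months (approximately 5 half-lives) following the last dose of IP", with the 3-month limb reserved for early withdrawal. For a completer, the reporting period therefore ends when study follow-up ends, and that date depends on which rule is used.

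**Working it through.** **Inputs.** Last scheduled IP: Week 44, Day 309 (Table 3). Week 48 visit: Day 337, no IP (Table 3). Follow-up visits: Days 365 and 393 (Table 4). Windows: ±3 days for treatment visits and ±7 days for follow-up visits. Placebo is listed as an investigational product in Table 6, so the Day 309 anchor holds in all three groups.

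**Step 1: check the calendar.** Every visit in Tables 3 and 4 satisfies day = 7 × week + 1. For example, 7 × 44 + 1 = 309, 7 × 52 + 1 = 365 and 7 × 56 + 1 = 393. The day and week rows agree with each other.

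**Step 2: try to reproduce the footnote's 4 and 8 weeks.** Interval in weeks = (visit day − anchor day) / 7.

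| Anchor | First visit, Day 365 | Second visit, Day 393 |
|---|---|---|
| Last IP, Week 44 (Day 309) | 56/7 = 8.0 | 84/7 = 12.0 |
| Week 48 visit (Day 337), no IP | 28/7 = 4.0 | 56/7 = 8.0 |

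The footnote's figures come out only from the second row, but the anchor it names is the first.

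**Step 3: apply the footnote literally.** 309 + 28 = Day 337 and 309 + 56 = Day 365. Day 337 is already Visit 14, the Week 48 end-of-treatment visit. Day 365 becomes the last visit, and Day 393 drops out: 393 − 365 = 28 days less follow-up.

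**Step 4: can the visit windows close the gap?**

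- First visit: earliest (365 − 7) − (309 + 3) = 46 days; latest (365 + 7) − (309 − 3) = 66 days. The footnote requires 28.
- Second visit: earliest (393 − 7) − (309 + 3) = 74 days; latest (393 + 7) − (309 − 3) = 94 days. The footnote requires 56.

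Neither range contains the footnote's value. A missed Week 44 dose widens the gap: from Week 40 (Day 281) the visits are 84/7 = 12 and 112/7 = 16 weeks after the last dose.

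**Step 5: compare with participants who discontinue IP.** Their minimum is 12 weeks after the last dose. Table 4's days give completers 12.0 weeks, which equals that minimum. The literal footnote gives them 8, which is 4 weeks less.

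**The case against.** The strongest reply is that this is a slip of wording in one sentence. Week 56 or Day 393 is the end of follow-up in the synopsis, Protocol 4.1, 6.1 and 6.4.4, exclusion criterion 7, SAP 2.2 and Table 4's own columns. Another footnote to Table 4, on lupus anticoagulant, also names Days 365 and 393. The literal reading is awkward too, because it places the first follow-up visit on the Week 48 visit. A site using the table would see explicit days, weeks and visit numbers. Most of this stands, and it limits the point in four ways.

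- **Length of the period.** A reader might infer that the length of safety follow-up is itself contradictory. It is not: the 8 weeks from Week 48 to Week 56 are stated consistently. Only the interval after the last dose conflicts.
- **Differences between sites.** A reader might infer that sites will follow participants for different lengths of time. The documents do not show this; it would require a site to set aside the column headers.
- **Who is affected.** A reader might count 4 lost weeks for every participant. Participants who discontinue IP but remain in the study have their own rule, and extension entrants skip these visits. Only completers who do not enter the extension are affected, and the documents do not say how many that will be.
- **Residual drug.** Section 8.2.3 equates 3 months with about 5 half-lives, so a reader might convert 8 and 12 weeks into percentages of drug remaining. In these documents that would rest on a half-life back-calculated from a rounded margin, and it has no meaning for placebo. In the Q12W group, if active doses fall at Weeks 0, 4, 12, 24 and 36 (an assumption from the regimen description), the visits are (365 − 253)/7 = 16 and (393 − 253)/7 = 20 weeks after the last active dose. No such percentages are claimed here.

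What the reply does not remove is that the footnote is the operative sentence giving the timing of these visits relative to dosing, and it disagrees with the table to which it is attached.

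**Conclusion.** This is an internal inconsistency in current text. For completers, the footnote's 4 and 8 weeks after the last dose conflict with the 8 and 12 weeks that follow from Tables 3 and 4. The difference is 28 days at each visit, and the visit windows do not absorb it.

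Followed literally, the footnote would end follow-up at Day 365, leave out the Day 393 assessments and give completers less post-dose follow-up than participants who discontinue IP. The point rests only on the Table 3 dosing row and the Table 4 visit days; no pharmacokinetic assumption is needed.

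That the footnote meant to count from the Week 48 visit is the simplest explanation of the arithmetic. It is still an inference, and the documents do not confirm it. The primary endpoint, sample size, randomisation and analysis sets are unaffected. The correction is worth making because the sentence governs when safety data are collected.

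**What to change.** Reconcile the Table 4 footnote with the Table 3 dosing schedule and the Table 4 visit days, so that a single anchor and a single interval are stated. The sponsor's clinical team must say which interval after the last dose is intended. If the Table 4 days stand, Section 6.1, Section 6.4.4 and SAP 2.2 need no change. If the footnote's interval stands, Table 4 and every statement that follow-up runs through Week 56 or Day 393 must be revised to match, and the at least 12 weeks set for participants who discontinue IP should be reviewed alongside it.

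If the days stand, the cost is one sentence in a protocol amendment, with no effect on sample size or on the analysis of the primary endpoint.
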